1.3 Dose Rationale and Risk/Benefits

Drug selection and dose rationale: In our rat studies, an allopurinol dose of 65 mg/kg/day (~300mg/day in humans) (134) effectively reduced AT1R and superoxide concentrations in the

Version: 23, 7-25-17

rat CCR (see Preliminary Studies). Subjects in our study will take allopurinol 300 mg daily for six weeks (dose will remain unchanged during four-week period). Allopurinol is quickly converted in vivo to its active metabolite, oxypurinol. Oxypurinol is responsible for the majority of the effects of allopurinol and has a half-life of 17-21 hours (135). Steady state blood concentrations of oxypurinol occur in approximately 105 hours (4.4 days). A study demonstrating vascular benefits of XO inhibition in patients with OSA was two weeks in duration, and our rat study used two weeks of CIH. We propose to have subjects take six weeks of study medication to increase the likelihood of observing significant sympathetic, vascular and blood pressure changes and to determine if preliminary changes seen after two weeks are sustained. A 300 mg daily dose will sufficiently inhibit XO because the IC₉₀ of oxypurinol for XO is approximately 5 µg/mL, and a single 300 mg dose of allopurinol produces peak levels of 5-7 µg/mL (136-138). At steady state, peak drug concentrations are higher than peak concentrations from single doses, and > 90% of XO will be inhibited. Losartan will be used in the doses that are clinically used to treat hypertension (50-100 mg daily by mouth). E-3174 is the active metabolite responsible for the clinical effects of losartan and E-3174 has a half-life of 4-9 hours (139). Thus, steady-state concentrations of E-3174 are quickly achieved after approximately 20-45 hours (139). Use of this dose is based on data demonstrating that 100 mg doses produce plasma concentrations > 1000 ng/mL of E-3174 (140). The ability of E-3174 to block the pressor effects of an intravenous angiotensin II challenge plateaus between 500-750 ng/mL (141). Thus, we feel our proposed doses will effectively block the actions of A-II.

We have chosen a six week treatment period because in our previous study, vascular endothelial function was improved after 6 weeks of treatment and did not further improve after 12 weeks of treatment. Furthermore, three weeks of losartan therapy successfully prevented chemoreflex sensitization in adult male, Sprague-Dawley rats.

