3.1 General Design

The proposed project is a randomized, double-blind, placebo-controlled, parallel three-treatment arm phase II clinical evaluation of allopurinol, losartan, and placebo in hypertensive patients with severe OSA. The proposed trial is based on preliminary data suggesting that both of these available medications may reduce chemoreflex sensitivity and endothelial function in patients with OSA. Subject enrollment will be conducted on a rolling basis during the three year study period and subjects will be randomized (stratified by baseline CPAP adherence) to one of the three treatments. Randomization will be stratified based on three categories of baseline CPAP

Version: 23, 7-25-17

adherence: < 1 hr, 1 – 4 hrs, and > 4hrs of CPAP use on average per night. This will ensure balanced CPAP use between treatment arms. Allopurinol will be initiated at 300 mg daily and the dose will remain constant for the six-week study session. Losartan will be initiated at 50 mg daily and the dose will be increased to 100 mg after two weeks if systolic blood pressure is above 120 mm Hg and as long as serum creatinine and potassium do not significantly increase. Subjects with SBP between 120-100 mm Hg may increase to 100 mg if approved by physician. If the subject's serum creatinine (> 0.5 mg/dL) or serum potassium (above 5.0 mEq/L) significantly increase, or if the subject experiences a significant side effect from the medication (e.g. maculopapular rash) the subject will be discontinued from the study. If the subject does not tolerate the losartan dose increase to 100 mg, his/her dose will be reduced back to 50 mg by study staff at request of subject. If the subject tolerates the dose increase, the losartan dose will then remain unchanged from the second to sixth week of the study. Patients in the placebo group will receive placebo capsules daily for six weeks that are identical in appearance to the overencapsulated losartan and allopurinol.

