Subjects will have 24-hour ambulatory blood pressure and 24-hour Holter/Heart rate variability measurements taken* (Visit 2) on a day/night prior to Visit 3. Prior to starting study drug therapy, subjects will come to the Clinical Research Unit (CRU) at the University of Wisconsin for physiology/vascular study (Visit 3). Subjects recruited from the other recruitment sites will come to Madison for Visit 3. Subjects will arrive on day one of their study, and will have physiologic assessments taken before full overnight polysomnography and overnight Holter/Heart rate variability* is completed during night one (to determine severity of OSA). Prior to polysomnography, subjects will have muscle sympathetic nerve activity, forearm blood flow, cerebral blood flow velocity, plasma catecholamines, ventilation, blood pressure, and heart rate measured at rest under normoxic (room air) conditions and during graded levels of hypoxia (90%, 85% and 80% SaO₂). Following this, subjects will be allowed to return to normoxia (room air levels of oxygen ~ 21% oxygen) and after dinner will be hooked up for polysomnography and Holter/Heart rate variability*. The morning after polysomnography, subjects will have assessment of brachial artery flow-mediated vasodilation and nitroglycerin induced vasodilation measured by ultrasound. Then subjects will have aortic pulse wave velocity and augmentation index measured by arterial tonometry. The 2nd night subjects will stay overnight again in the VA Research Unit and have control of breathing studies completed (Pcrit and apnea threshold). Subjects will initiate study drug treatment and will return two weeks later for a blood pressure and heart rate (office blood pressure) measurement, CPAP assessment, and safety assessment to measure serum creatinine and serum potassium concentrations. This is standard safety monitoring in patients taking ARBs, and to maintain blinding, all subjects will have this monitoring completed. Subjects who do have clinically significant increases in serum creatinine (an increase > 0.5 mg/dL) or whose serum potassium increases to a concentration > 5.0 mEq/L will have their participation in the study terminated. Subjects continuing in the study will then complete four additional weeks of drug therapy. At the end of six weeks of study medication, subjects will have 24-hour ambulatory blood pressure and 24-hour Holter/Heart rate variability assessed one day and night.

Version: 23, 7-25-17

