4.2 Exclusion Criteria

Exclusion Criteria

- If subject not using CPAP, having AHI $>$ 60 events/hour or oxygen saturation \leq 65% during sleep
- Presence of clinical CV disease (coronary artery disease, angina, arrhythmias (subjects with sinus arrhythmias will be reviewed by PI for enrollment), stroke, TIA, cor pulmonale, etc.), heart failure, bruits, or diabetes mellitus by clinical diagnosis/history
- Presence of pulmonary disease that results in significant hypoxemia (resting SaO₂ $<$ 88%)
- Hypertriglyceridemia (triglycerides $>$ 300 mg/dL).
- Diabetes (fasting plasma glucose $>$ 125 mg/dL)
- Subjects taking angiotensin converting enzyme inhibitors, angiotensin receptor antagonists, renin inhibitors, potassium-sparing diuretics (without accompanying loop/thiazide diuretic), allopurinol, oxypurinol, febuxostat, amoxicillin, ampicillin, azathioprine or mercaptopurine. *(see below for examples)
- Subjects with chronic kidney disease (Serum creatinine $>$ 1.5 mg/dL) or history of significant hyperkalemia (Serum potassium $>$ 5.2 mEq/L) with ARB therapy
- Subjects with history of angioedema
- Subjects with bilateral, modified radical or radical mastectomies
- Subjects who have a Serum potassium $>$ 5.0 mEq/L at the screening visit
- Female subjects who are pregnant (determined by urine pregnancy test) or breastfeeding
- Subjects with active MRSA or VRE (vancomycin resistant enterococcus) infection
- History of adverse reaction to allopurinol, losartan, or zolpidem**
- Subjects who are currently receiving cancer treatment or have received cancer treatment in the past 1 year.
- Subjects who cannot swallow oral capsules
- Subjects who are hospitalized or who have been recently hospitalized (last 2 weeks)

Version: 23, 7-25-17

- Inability to comply with or complete the protocol or other reasons at the discretion of the investigators

*angiotensin converting enzyme inhibitors (lisinopril, enalapril, etc.)

Angiotensin receptor antagonists (losartan, valsartan, etc.)

Renin inhibitors (aliskiren)

Potassium sparing diuretics (spironolactone, eplerenone, triamterene without hydrochlorothiazide, etc.)

**If adverse reaction to zolpidem, may opt out of control of breathing study

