4.4 Early Withdrawal of Subjects

4.4.1 When and How to Withdraw Subjects

Allopurinol

If a subject experiences an adverse effect that is thought to be significant or serious (e.g. renal impairment, maculopapular rash, etc.) subjects' participation in the study will be ended.

Losartan

If a subject experiences clinically significant/serious adverse effects (angioedema, myalgias, acute renal failure), their participation will be ended. If the subject experiences increases in serum creatinine (> 0.5 mg/dL) or serum potassium (above 5.0 mEq/L) the subject's participation in the study will be ended. Blood pressure will also be measured at the two week monitoring visit (Visit 4). The dose of losartan will increase to 100mg daily if systolic blood pressure is > 120 mm Hg. For a systolic blood pressure between 100-120 mm Hg the subject may have dose increased if approved by study physician. If the subject's blood pressure is $< 100/60$ mm Hg and if the patient is dizzy and symptomatic during the study, the subject will discontinue study medication and go off study. This can be done via a phone encounter or via an additional (unexpected) visit. It is possible the subject's participation will be terminated if the study physicians feel that is appropriate.

Subjects may also be withdrawn from the study if they are diagnosed with a new and significant medical problem (e.g. they are hospitalized for an acute illness or major medical condition). Subjects may also be withdrawn from the study if they consistently fail to adhere to the protocol requirements. Study physicians will communicate with subjects' regular physician about care plans upon their withdrawal from the study.

Version: 23, 7-25-17

Additional (Unexpected) Visit:

If a subject experiences an adverse event that requires them to be seen by study staff, they should be scheduled for a visit to their local center as soon as is feasible. The PIs should be notified immediately and the physician at the local site should see the subject during the visit. Depending on the complaint, the AE should be evaluated with appropriate objective measures (blood tests, blood pressure/heart rate measurements, etc.) and the case report forms for "Additional Visit" should be filled out (in subject binder). These forms include:

AE form
Vitals form
Additional visit form
AE log

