5.2 Treatment Regimen

Losartan 50 mg daily for two weeks, then increased to 100mg daily for 4 weeks

OR

Allopurinol 300 mg daily for 6 weeks

OR

Placebo capsule daily for 6 weeks

All three medications will be taken orally (in capsules) by subjects. The treatment regimen is summarized in Table 1.

Table 1. Treatment Regimen

Version: 23, 7-25-17

Arm	Treatment	Administered as:			
		Active Losartan 50mg Capsule Bottle A	Active Losartan 100mg Capsule Bottle B	Placebo	Allopurinol 300mg Capsule
Group I	Losartan	1 capsule daily on Days 1-14	1 Capsule daily on Days 15-42	None	None
Group II	Allopurinol	None	None	None	1 Capsule Daily on Days 1-42
Group III	Placebo	None	None	1 Capsule Daily on Days 1-42	None

Losartan subjects will take capsules from Bottle A for days 1-14, and capsules from Bottle B for days 15-42. If the subject's systolic blood pressure is > 120 mm Hg, the subject will continue to take capsules daily from Bottle A (days 15-42). If SBP is between 100-120 mm Hg, the subject may switch to bottle B with physician approval.

Allopurinol and Placebo will also have Bottle A and B for each treatment and will contain identical drug in Bottle A and Bottle B. Subjects will transition from Bottle A to Bottle B after day 14 in the allopurinol and placebo group. This is done to maintain study blinding.

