6.3 Sample collection

Blood samples collected during Visits 1 and 4 will be processed for the specific laboratory parameter at the local site and assayed in the clinical labs (or couriered from LaCrosse to Marshfield to be assayed). Samples will be collected and sent to the clinical laboratory for measurement of serum creatinine, serum potassium, serum glucose, lipid panels, serum uric acid, etc. At Visits 3 and 6 at UW-Madison, blood samples will be drawn at rest while the subject is breathing room air. Uric acid will be collected and assayed in the UW Hospital and Clinics Clinical Laboratory and other samples will be collected for research use. These samples collected for research use will be centrifuged, aliquoted, and stored in the locked freezer space at the University of Wisconsin School of Pharmacy for future assay. Stored blood samples will be stripped of identifiers and only labeled with study subject number and Visit number. Plasma will be sent to the TTR Analytical Laboratory Core at the University of Iowa College of Pharmacy for plasma catecholamine measurement. Other plasma will be assayed at the UW School of Pharmacy for oxidative stress markers.

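### No creatinine or potassium test is named after week 2, so none covers losartan 100 mg unless Appendix 1 or 2 schedules one at Visit 6

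*Combined protocol and SAP*

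**What the plan says.** Section 3.1 starts losartan at 50 mg and raises it to 100 mg after two weeks, depending on systolic pressure and "as long as serum creatinine and potassium do not significantly increase". The treatment table in 5.2 gives the 100 mg bottle as "1 Capsule daily on Days 15-42".

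Creatinine and potassium are measured at screening (4.3) and at the two-week visit (3.1). Of the two-week test, 3.1 says: "This is standard safety monitoring in patients taking ARBs, and to maintain blinding, all subjects will have this monitoring completed". Section 4.4.1 states the consequence of an abnormal result: "increases in serum creatinine (> 0.5 mg/dL) or serum potassium (above 5.0 mEq/L) the subject's participation in the study will be ended". Section 8.1 treats a creatinine rise of more than 0.4 mg/dL as an example of a laboratory adverse event.

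For Visit 6, 6.2 lists blood samples without naming analytes. Section 6.3 is more specific about Visits 3 and 6: "Uric acid will be collected and assayed in the UW Hospital and Clinics Clinical Laboratory and other samples will be collected for research use". Section 5.5 adds plasma renin activity at baseline and week 6, as an indirect adherence measure. Visit 7 is a telephone call (6.2).

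For an unscheduled visit after an adverse event, 4.4.1 says "the AE should be evaluated with appropriate objective measures (blood tests, blood pressure/heart rate measurements, etc".

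**The concern.** The week-2 test comes before the dose increase and helps decide it, so it cannot show what the higher dose does to renal function or potassium. The plan itself regards these two tests as the standard safety check for this drug class, yet names neither once the dose has doubled.

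At stake is the detection of a symptomless rise on 100 mg. Section 8.2 provides for specific questioning at each contact, and 6.2 includes a physical examination at Visit 6, but neither measures creatinine or potassium. There would also be no laboratory safety comparison by arm at the end of treatment. Week-2 values can be reported by arm, but for losartan they describe 50 mg. The stored research samples are not planned for these analytes, and a later assay would come too late for follow-up.

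**Working it through.** The plan gives no figure to reproduce. The check is a trace of every scheduled visit against the losartan dose.

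| Visit | Timing and losartan dose | Creatinine and potassium named? | Source |
|---|---|---|---|
| 1 | Screening, no drug | Yes, both | 4.3 |
| 1A | Before treatment, only if Visit 2 is more than 90 days after Visit 1 | Screening bloods repeated | 6.2 |
| 2 | Before treatment | No: ambulatory pressure, adverse events | 6.2 |
| 3 | Baseline, drug dispensed | No: uric acid, renin activity, research samples | 5.5, 6.3 |
| 4 | Week 2, 50 mg | Yes, both | 3.1 |
| 5 | End of six weeks, 50 or 100 mg | No: ambulatory pressure, adverse events | 6.2 |
| 6 | Week 6, 50 or 100 mg | No: uric acid, renin activity, research samples, unspecified blood samples | 5.5, 6.2, 6.3 |
| 7 | One month after treatment | No: telephone | 6.2 |

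**Which visits the chemistry sentence in 6.3 covers.** The sentence listing creatinine, potassium, glucose, lipids and uric acid carries no visit number. It directly follows a sentence about Visits 1 and 4 and precedes one about Visits 3 and 6, which names uric acid again. If the full list applied to every visit, that second mention would be redundant. Reading the list as Visits 1 and 4 only is an inference, but the more natural one.

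**What Visit 4 measures.** Section 1.3 says "steady-state concentrations of E-3174 are quickly achieved after approximately 20-45 hours". That is 20/24 = 0.8 to 45/24 = 1.9 days, so by week 2 the values reflect steady state on 50 mg.

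**Time at 100 mg without a named test.**
- Days 15 to 42: 42 - 15 + 1 = 28 days, and 28/42 = 67% of treatment.
- With a first 100 mg dose on day 15, steady state is reached by about day 17. Days 17 to 42: 42 - 17 + 1 = 26 days.
- Scheduled tests named during or at the end of this period: 0. With the fix: 1 per subject who attends Visit 6.

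**How many subjects.** 100 randomised (7.1) divided by 3 arms is about 33 on losartan, assuming equal allocation, which the text does not state. This is a ceiling. The number reaching 100 mg is unknown, because 3.1 and 4.4.1 raise the dose when systolic pressure is above 120 mm Hg while the text of 5.2 keeps those subjects on Bottle A (50 mg).

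**Potassium margin at entry.** Section 4.2 excludes potassium above "5.0 mEq/L at the screening visit", so 5.0 is eligible, and participation ends above 5.0. The smallest margin is 5.0 - 5.0 = 0 mEq/L.

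**The case against.** **The visit table is missing.** Section 6 refers to Appendix 2, the table of procedures and visits, where Visit 6 analytes would normally be listed. Neither it nor Appendix 1 could be read. Section 6.3 is not exhaustive: it omits the week-6 renin activity given in 5.5. A reader might infer that the trial has no end-of-treatment safety chemistry. The documents do not support that as a flat statement, so the point stands only on condition that the appendices are silent.

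**The withdrawal limits belong to week 2.** A reader might infer a withdrawal rule meant to run for all six weeks with no data behind it. The text does not support this. Section 3.1 states the limits directly after the two-week test and then sends continuing subjects on for four more weeks. Section 4.4.1 goes straight from the limits to the blood pressure measured at the same visit. The limits read mainly as a continuation and titration gate, and the test that gate needs is scheduled. What remains is narrower: after the gate, no test of the higher dose is named.

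**The week-2 check is adequate as it stands.** The dose is in the usual clinical range, and 4.2 excludes creatinine above 1.5 mg/dL, potassium above 5.0 mEq/L at screening, diabetes and other drugs acting on the same system. A subject entering at 5.0 is retested before any increase. These points lower the risk, and no section requires a repeat test after titration. They do not make a test on 50 mg informative about 100 mg.

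**A Visit 6 test protects nobody during treatment.** This is correct. Study drug is collected at that visit. The gain is follow-up of abnormal values and a comparison by arm.

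**Conclusion.** The point holds conditionally, as a cheap improvement. In the text available, the last scheduled creatinine and potassium test is at week 2 on 50 mg, and none is named for the 28 days planned at 100 mg. A symptomless rise on that dose would be found only if an adverse event prompted an additional visit.

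This rests on two assumptions: that neither Appendix 1 nor Appendix 2 lists the tests at Visit 6, and that the chemistry sentence in 6.3 refers to Visits 1 and 4. If the first is wrong, there is no safety gap.

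The figure of about 33 should not be read as the number exposed to 100 mg without testing. It is the whole losartan arm under assumed equal allocation. Because 7.1 reports interim data, some subjects have probably already passed Visit 6, and the number who could still benefit is unknown.

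**What to change.** First check Appendices 1 and 2. If either lists creatinine and potassium at Visit 6, no safety change is needed, and aligning 6.3 with it is only clerical.

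If neither does, amend 6.3 to add serum creatinine and potassium, in all arms so that the blind is kept, to the Visit 6 blood already sent to the hospital clinical laboratory for uric acid. Follow up abnormal values under 8.1 and 8.2. Report change from baseline by arm, taking the last pre-treatment value (Visit 1 or 1A) as baseline because neither analyte is named at Visit 3. Also report the number beyond the 4.4.1 and 8.1 limits.

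The cost is an amendment and two routine assays per remaining subject, with no new visit: at most 2 x 100 = 200 assays, and fewer to the extent that subjects have already completed. Detection comes at the end of treatment only. Acting on the limits during days 15-42 would need a test in weeks 3-5, a separate decision for the sponsor.

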6.4 Study communication and oversight

At the start of the trial, study binders will be set up for each study site with the current protocol version (will include protocol number and date). At any time during the study when the protocol changes, a new protocol will be sent to each site to be included in the study binder and to be kept in a relevant study folder electronically with the study coordinator. The new protocol will be sent along with a summary of protocol changes denoted separately to the study coordinator, the IRB and co-Investigators. Discussion of protocol changes will also be an item of discussion at the bi-weekly WiNHR coordinator conference calls.

When the UW HS IRB approves amendments to the protocol, copy of the approval will accompany the summary of changes approved and the new protocol version sent to the study sites. Electronic copies of the approval documents will be forwarded to each site with the other electronic documents and stored electronically and in paper form in an IRB folder at each study site. At each biweekly WiNHR coordinator conference call, reconciliation of all current approvals will be performed by all the investigators and their study binders and electronic files.

Reporting of adverse events and unanticipated problems will be performed at all centers through the Principal Investigators to comply with the UW HS IRB requirements. Investigators at all study sites will be instructed to notify the Principal Investigators of all adverse events immediately upon awareness of their occurrence. The Principal investigators and the study coordinator in Madison will provide the information to the DMC and the IRB in the appropriate

Version: 23, 7-25-17

time frame. Unanticipated problems will be discussed at each WiNHR biweekly coordinator conference call and at quarterly investigator meetings.

For events that are unexpected, immediately life threatening or severely debilitating to other current subjects, and caused by or probably related to the study drug, the DMC and IRB will be notified immediately.

Any deviations from the protocol at any of the research sites will be discouraged and if occur, will be reported to the UW HS IRB if the deviation or exception presents a significant safety risk to the subject or potential subject. As per Good Clinical Practices, protocol deviations will be documented and reviewed at the quarterly investigator meetings. If changes are necessary for the project, protocol modifications will be submitted to the HS IRB to change the protocol to fit the required changes.

6.5 *Unexpected Findings*

Whenever tests like the electrocardiogram (Visit 1), cardiac output (Visits 3 and 6), or serum laboratory tests are done, there is the chance of an unexpected finding. Subjects will be informed of all findings of clear clinical significance which may be revealed during the electrocardiogram, cardiac output procedure (limited echocardiography), and serum laboratory tests. Findings of clear clinical significance are those for which we generally know the risks of non-treatment and for which treatment may be available. If unexpected findings for the electrocardiogram, cardiac output, or serum laboratory tests are discovered, a letter describing the findings will be sent to the subject and to his/her physician with permission from the subject.

7 Statistical Plan

7.1 *Sample Size Determination*

The primary outcome will be the change in the slope response of MSNA during progressive hypoxia from baseline to 6 weeks. From previous data from our lab we have seen an approximate standard deviation for slope in OSA patients under similar progressive hypoxia of 8-10.

Based on interim data, a power calculation for the differences and standard deviations in primary outcome variable estimated that we would have 90% power (this is increased power from our original sample size calculation that used 80%) to determine a difference of 3.07 (1.13 vs -1.94) at a significance level of 0.017 (Bonferroni adjusted alpha for 3 tests) if we had complete MSNA slope response data from 20 subjects per group.

We had originally proposed to enroll 50 subjects per group. Our interim analysis determined that if we obtain complete data in 20 subjects per group, we are likely to find a significant difference. We will enroll as many subjects as we can in the remaining time frame to give us the best possible chance at finding a difference. Consistent with DMC recommendations, we will reduce our sample size to 100 subjects. To account for drop-outs, we will ask to enroll 120 subjects to get 100 subjects who proceed to randomization.

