3.2 Primary Study Endpoints

The primary outcome variable is the difference in the individual slope of the MSNA – SaO₂ response curve at 6 weeks and baseline between treatment groups. Basal normoxic MSNA and MSNA responses during hypoxia will be compared between the three treatment groups. For purposes of quantification, MSNA is expressed as burst frequency (bursts/min), burst amplitude (arbitrary units) and total minute activity (burst frequency x mean burst amplitude). Total minute activity of mSNA is an effective way to capture the change in both burst frequency and burst amplitude. Both amplitude and burst frequency are influenced by disease states such as OSA and by environmental conditions such as hypoxia. Postganglionic mSNA in the right peroneal nerve will be recorded directly using the microneurography technique (95). The neural signals are passed to a differential preamplifier, an amplifier, a band-pass filter, and an integrator (time constant=100 ms). Placement of the recording electrode within a muscle nerve fascicle is confirmed by the presence of muscle twitches in response to electrical stimulation, the appearance of afferent activity in response to tapping or stretching of muscle, but not gentle stroking of skin, in the appropriate receptive fields, and other criteria. Once an acceptable neural recording (signal-to-noise ratio >3:1) is obtained, the subject is instructed to maintain the leg in a relaxed position for the duration of the study. Sympathetic bursts will be identified by computer-assisted inspection of the mean voltage neurogram.

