7.2 Statistical Methods

Data will be analyzed by a statistician blinded to drug assignment. Demographic comparisons to assess effectiveness of randomization will be examined between treatment arms by ANOVA and chi-square tests where appropriate. Differences in baseline values for all variables between treatment arms will be assessed using ANOVA. The paired differences in these same variables will be compared after the 6-week study period. These values include all measured physiologic variables, such as resting heart rate, blood pressure, plasma catecholamine concentrations, MSNA, cerebral blood flow, forearm blood flow, flow-mediated vasodilation, pulse wave velocity, augmentation index, polysomnographic measures, Pcrit, apnea threshold, and others.

The primary outcome variable is the difference in the individual slope of the MSNA – SaO₂ response curve at 6 weeks and baseline between treatment groups. The MSNA – SaO₂ response curve will be graphed with MSNA as the dependent variable and SaO₂ as the independent variable during progressive hypoxia. Slope response curves will also be calculated for heart rate, ventilation, forearm blood flow, cerebral blood flow, and blood pressure during hypoxia, hyperoxia and controlled breathing periods. MSNA will be expressed as burst frequency (bursts/min), burst amplitude (arbitrary units) and total minute activity (burst frequency x mean burst amplitude). MSNA will be averaged over the 5-min measurement periods at baseline, 90%, 85%, 80% hypoxia, and during controlled breathing. During hyperoxic trials, 15-sec averages of MSNA will be obtained, and an average of the 4 trials will be computed. The slope response of MSNA during progressive hypoxia will be calculated and will be analyzed using ANOVA. Changes in polysomnographic measures from baseline to the end of the 6-week treatment period between the treatment groups will be compared using ANOVA. If significant ANOVA p-values are found, then post-hoc multiple comparison Tukey HSD tests will examine differences between each arms. Multiple regression will be used to determine the influence of subject characteristics and hours of CPAP use on the primary outcome, and on the effect of treatment on the primary outcome.

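### Is the 90% power at 20 per group contradicted by the slope SD of 8-10 printed just above it?

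*Combined protocol and SAP*

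**What the plan says.** Section 7.1 defines the primary outcome as the change in MSNA slope during progressive hypoxia from baseline to 6 weeks. It gives one SD, from the laboratory's earlier data: an "approximate standard deviation for slope in OSA patients under similar progressive hypoxia of 8-10".

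A separate paragraph gives the current calculation: "Based on interim data, a power calculation for the differences and standard deviations in primary outcome variable estimated that we would have 90% power", namely power "to determine a difference of 3.07 (1.13 vs -1.94) at a significance level of 0.017 (Bonferroni adjusted alpha for 3 tests"), with complete slope data from 20 subjects per group. It adds that the first sample size calculation used 80% power.

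The section then draws on the result: "Our interim analysis determined that if we obtain complete data in 20 subjects per group, we are likely to find a significant difference". The original target was 50 per group. The new target is set with the data monitoring committee: "Consistent with DMC recommendations, we will reduce our sample size to 100 subjects". For losses, "we will ask to enroll 120 subjects to get 100 subjects who proceed to randomization".

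On the scale of measurement, Section 7.2 says "MSNA will be expressed as burst frequency (bursts/min), burst amplitude (arbitrary units) and total minute activity (burst frequency x mean burst amplitude"). Section 3.2 lists the same three and remarks that "Total minute activity of mSNA is an effective way to capture the change in both burst frequency and burst amplitude", but neither section makes one of them the primary scale.

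The interim SD, the number of subjects behind it, the pre/post correlation and the sidedness of the test are not printed.

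**The concern.** The only SD a reader can see is 8-10, and the effect to be detected is 3.07. If 8-10 were the SD of change, 20 per group would give power near 10%, and 90% would need 183 to 286 per group by the normal approximation. Even read as the SD of a single slope, it yields 90% at 20 per group only if the baseline and 6-week slopes correlate at about 0.95 or more, which is high for a slope fitted to a few oxygen-saturation levels.

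The calculation is one of the reasons given for going from 50 per group to 100 in total. If the 90% were wrong, the reduced trial could be badly underpowered for its primary outcome, and the statement that a significant result is likely would mislead.

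**Working it through.** **Inputs from Section 7.1.** Difference 1.13 − (−1.94) = 3.07. Alpha 0.05/3 ≈ 0.017. n = 20 per group with complete data. Stated power 90%. Slope SD 8-10 from earlier data. Total randomised 100, so 100/3 ≈ 33 per group.

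**Assumptions not in the plan.** Two-sided test; equal SD of change across arms; for the correlation step, equal slope variance at both visits.

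**Step 1: can the plan's 90% be reproduced?** Not directly, because the interim SD it used is not printed. It can be solved for. By the normal approximation,

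SD = 3.07 / [(z₁₋α/₂ + z₀.₉₀) × √(2/20)] = 3.07 / [(2.387 + 1.282) × 0.3162] = 2.65.

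The noncentral t with 38 degrees of freedom gives 2.55; with error pooled over three arms (57 df), 2.58. One-sided testing gives 2.77 (t). A three-group ANOVA F-test at 0.017 gives 2.35 to 2.71, depending on the third mean. So the stated power implies an SD of change of roughly 2.3 to 2.9.

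**Step 2: what if 8-10 were the SD of change?** Power at 20 per group is 11% (SD 8) to 7% (SD 10), and at 33 per group 19% to 12%. No variant in Step 1 comes near 8-10.

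**Step 3: 8-10 as the SD of a single slope.** With SD_change = SD_slope × √[2(1 − r)],

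r = 1 − SD_change² / (2 × SD_slope²).

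- SD_slope 8: r = 1 − 2.546²/128 = 0.949
- SD_slope 10: r = 1 − 2.546²/200 = 0.968

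At lower correlations, taking SD_slope 8 to 10, power at 20 per group is 59% to 38% (r = 0.9) and 30% to 18% (r = 0.8). All of this holds only if 8-10 and 3.07 are on the same MSNA scale, which the plan does not say.

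**Step 4: is 8-10 an input at all?** The two figures differ on each point that matters:

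| | SD of 8-10 | SD behind the 90% |
|---|---|---|
| Source | earlier laboratory data | this trial's interim data |
| Quantity | slope | primary outcome, i.e. change in slope |
| MSNA scale | not named | not named |
| Value printed | yes | no |

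The text attributes the 90% to the right-hand column. Steps 2 and 3 therefore test a calculation that the plan does not claim to have made.

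**Step 5: margin in the planned size.** Power for 3.07, two-sided alpha 0.017, t-test:

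| SD of change | 20 per group | 33 per group |
|---|---|---|
| 2.5 | 91% | 99% |
| 3 | 77% | 95% |
| 3.5 | 61% | 86% |
| 4 | 48% | 75% |
| 5 | 30% | 52% |

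The largest SD of change giving 90% is 2.55 at 20 per group and 3.32 at 33. For 80% the limits are 2.89 and 3.78. Falling from 33 to 20 evaluable means losing (33 − 20)/33 ≈ 39% after randomisation.

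**The case for a change.** The strongest case for a change is that the operative SD is missing while one that looks incompatible stands beside it without explanation. Naming neither the scale nor the sidedness makes matters worse: if the scales differ, the section prints no usable SD at all. That is true, and it is what survives of the concern.

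An interim SD is also only an estimate. If it were exactly 2.55 from an assumed total of 15, 30 or 50 subjects in three arms (the plan does not give the number), its upper 95% limit would be 4.20, 3.47 or 3.19, and power at 20 per group would be 44%, 62% or 71%. These figures show one side only. The lower limits are 1.83, 2.01 and 2.12, where power is about 98% or more. At 33 per group the upper limits give 70%, 87% and 92%. The exercise rests on an assumed interim size, so it shows that the 90% is uncertain, not that it is wrong.

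Finally, 33 evaluable per group is an upper bound. The allowance from 120 to 100 is spent before randomisation, and Section 6.2 lets subjects omit procedures. That stands. Section 7.3 partly offsets it, since a subject who cannot finish the hypoxia protocol still contributes a slope from the data obtained.

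**Conclusion.** The arithmetic behind the concern is right: 90% at 20 per group needs an SD of change of about 2.55. It does not show an error in the plan. The 8-10 is an SD of a different quantity from a different source, possibly on another scale, and Section 7.1 does not say that it enters the calculation. An interim SD of change near 2.55 would give the stated power, and nothing in the documents rules that out.

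This is missing detail. The team holds the interim SD, and stating it with its MSNA scale would help a reader but would change no sample size, analysis or conclusion. The reduction to 100 also rests on the monitoring committee's advice and the remaining time, and about 33 per group are to be randomised against the 20 in the calculation. The conclusion assumes a two-sided test and similar SDs across arms. It does not certify the 90%, which cannot be checked from the documents.
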